5.2.4.2 Continuous ECG monitoring

Cardiac rhythm (including heart rate) will be monitored by means of continuous 2-lead ECG recording for at least 15 min before (for baseline assessment) and constantly for 4 h after start of infusion using the Dräger Telemetry monitoring system, Infinity M300.

5.2.5 Assessment of other safety parameters

5.2.5.1 Vital signs

Systolic and diastolic blood pressures (BP) as well as pulse rate (PR) or heart rate (heart rate is considered to be equal to pulse rate) will be measured by a blood pressure monitor (e.g. Welch Allyn 530TP and 530TO devices) at the times indicated in the [Flow Chart](#), after subjects have rested for at least 5 min in a supine position. All recordings should be made using the same type of blood pressure recording instrument on the same arm if possible.

Oral body temperature will be determined using a digital thermometer at the time points indicated in the [Flow Chart](#).

5.2.5.2 Medical examinations

At the screening visit, the medical examination will include documentation of subject information, informed consent, demographics including height and body weight, smoking and alcohol history, relevant medical history and concomitant therapy, review of inclusion and exclusion criteria, review of vital signs (BP, PR), 12-lead ECG, laboratory tests, and a physical examination. At the end of trial examination, it will include review of vital signs, 12-lead ECG, laboratory tests, and a physical examination.

5.2.5.3 Local tolerability

Local tolerability will be assessed by the investigator according to ‘swelling’, ‘induration’, ‘heat’, ‘redness’, ‘pain’, or ‘other findings’.

5.3 OTHER

Not applicable.

5.4 APPROPRIATENESS OF MEASUREMENTS

All measurements performed during this trial are standard measurements and will be performed in order to monitor subjects’ safety and to determine pharmacokinetic parameters and biomarkers in an appropriate way. The scheduled measurements will allow monitoring of changes in vital signs, standard laboratory values, and ECG parameters that might occur as a result of administration of trial medication. The safety assessments are standard, are accepted for evaluation of safety and tolerability of an intravenously administered drug, and are widely used in clinical trials. The pharmacokinetic parameters and measurements outlined in [Section 5.5](#) are generally used assessments of drug exposure. The biomarkers outlined in [Section 5.6](#) are of exploratory nature only.

5.5 DRUG CONCENTRATION MEASUREMENTS AND PHARMACOKINETICS

Date and clock time of drug administration and pharmacokinetic sampling will be recorded in the CRFs.

PK sampling times and periods may be adapted during the trial based on information obtained during trial conduct (e.g. preliminary PK data) including addition of samples and visits as long as the total blood volume taken per subject does not exceed 550 mL. Such changes would be implemented via non-substantial CTP Amendments.

5.5.1 Pharmacokinetic endpoints

The following pharmacokinetic parameters will be determined if feasible:

5.5.1.1 Secondary endpoints

- C_{\max} (maximum measured concentration of the analyte in plasma)
- AUC_{0-tz} (area under the concentration-time curve of the analyte in plasma over the time interval from 0 to the last quantifiable data point)
- $AUC_{0-\infty}$ (area under the concentration-time curve of the analyte in plasma over the time interval from 0 extrapolated to infinity)

Further pharmacokinetic parameters might be calculated as appropriate.

5.5.2 Methods of sample collection

5.5.2.1 Plasma sampling for pharmacokinetic analysis

For quantification of BI 655088 plasma concentrations, 2.7 mL of blood will be taken from an antecubital or forearm vein into a K₃-EDTA (tripotassium ethylenediaminetetraacetic acid)-anticoagulant blood drawing tube at the times indicated in the [Flow Chart](#). Blood will be withdrawn by means of either an indwelling venous catheter or by venipuncture with a metal needle. Within the first 6 hours following start of infusion, blood samples should be taken from the contralateral arm used for infusion.

The K₃-EDTA-anticoagulated blood samples will be centrifuged for about 10 min at about 2000 g to 4000 g and at 4 to 8 °C. Two plasma aliquots will be obtained and stored in polypropylene tubes. The first aliquot should contain at least 0.5 mL plasma. The process from blood collection until transfer of plasma aliquots into the freezer should be completed within 60 min, with interim storage of blood samples in ice water or on ice. For each aliquot the time when the sample was placed in the freezer will be documented. Until transfer on dry ice to the analytical laboratory, the aliquots will be stored upright at about -20°C or below at the trial site. The second aliquot will be transferred to the analytical laboratory after the bioanalyst has acknowledged safe arrival of the first aliquot. At the analytical laboratory the plasma samples will be stored at about -20°C or below until analysis.

At a minimum, the sample tube labels should list the following information: BI trial number, subject number, visit, and planned sampling time. Further information such as matrix and analyte may also be provided.

After completion of the trial the plasma samples may be used for further methodological investigations, e.g. for stability testing, assessment of metabolites. However, only data related to the analyte and/or its metabolite(s) including anti-drug antibodies (if applicable) will be generated by these additional investigations. The study samples will be discarded after completion of the additional investigations but not later than 5 years upon the final study report has been signed.

5.5.3 Analytical determinations

5.5.3.1 Analytical determination of BI 655088 plasma concentration

BI 655088 concentrations in plasma will be determined by a validated assay. All details of the analytical method will be available prior to the start of sample analysis.

As described in [Section 4.1.5](#), the bioanalyst will be unblinded during sample analysis.

5.6 BIOMARKERS

5.6.1 Biomarkers for assessment of target engagement

The pharmacodynamic (PD) assessment of this trial comprises determination of exploratory target engagement biomarkers:

5.6.2 Methods of sample collection

PD sampling times and periods may be adapted during the trial based on information obtained during trial conduct (e.g. preliminary PK/PD data), including addition of samples and visits, as long as the total blood volume taken from each subject does not exceed 550 mL. Such changes would be implemented via non-substantial CTP Amendments.

The laboratory should be contacted prior to shipment (

After completion of the study the samples may be used for further biomarker investigations, assay development and validation purposes, e.g. method comparison or sample stability studies. These analyses may be performed in laboratories other than Boehringer Ingelheim, Germany, if necessary. The study samples will be discarded after completion of any additional investigations but not later than 5 years after the CTR has been signed.

5.6.3 Analytical determinations

Samples will be measured at Boehringer Ingelheim, TMCP/TMBT, Biberach, Germany. Characteristics of the analytical methods will be given in the clinical study report.

Left over samples for biomarker analysis may be used for further assay development and validation purposes, e.g. method comparison or sample stability studies. These analyses may be performed in laboratories other than Boehringer Ingelheim, Germany, if necessary.

5.7 PHARMACOKINETIC - PHARMACODYNAMIC RELATIONSHIP

The PK and PD (biomarker) data from this study may be used for an exploratory investigation of PK/PD relationship of BI 655088.

6. INVESTIGATIONAL PLAN

6.1 VISIT SCHEDULE

Exact times of measurements outside the permitted time windows will be documented. The acceptable time windows for screening and end of trial examination are given in the [Flow Chart](#).

Oral glucose tolerance test at baseline may be done within 8 days prior to the drug administration, i.e. the acceptable deviation from Day -5 will be -3 days.

Study measurements and assessments scheduled to occur 'before' trial medication administration on Day 1 are to be performed and completed within a 3 h-period prior to the start of trial drug administration (including blank values for PK and biomarkers).

The acceptable deviation from the scheduled time for vital signs (BP, PR, and body temperature) and ECG will be:

- ± 15 min up to including 12 h
- ± 30 min from after 12h up to including 48 h

The acceptable deviation from the scheduled time for laboratory samples and bleeding time:

- ± 5 min up to including 2 h
- ± 15 min from after 2h up to including 12 h
- ± 30 min from after 12h up to including 48 h
- ± 120 min from after 48 h up to Day 8
- ± 4 hours from after Day 8 up to Day 29
- $\pm 1, 2$ or 3 days from after Day 29 up to the last measurement as indicated in the [Flow Chart](#)

If scheduled in the [Flow Chart](#) at the same time as a meal, blood sampling, vital signs and 12-lead ECG recordings have to be done first. Furthermore, if several measurements including venipuncture are scheduled for the same time, venipuncture should be the last of the measurements due to its inconvenience to the subject and possible influence on physiological parameters.

For planned individual plasma concentration sampling times refer to the [Flow Chart](#). While these nominal times should be adhered to as closely as possible, the actual sampling times will be recorded and used for determination of pharmacokinetic parameter. The same applies to biomarker sampling and pharmacodynamic parameters.

If a subject misses an appointment, it will be rescheduled if possible. The relevance of measurements outside the permitted time windows will be assessed no later than at the Report Planning Meeting.

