3.3.3 Exclusion criteria

Subjects will not be allowed to participate if any of the following general criteria apply:

1. Any finding in the medical examination (including BP, PR or ECG) is deviating from normal and judged as clinically relevant by the investigator
2. Repeated measurement of systolic blood pressure outside the range of 90 to 140 mmHg, diastolic blood pressure outside the range of 50 to 90 mmHg, or pulse rate outside the range of 45 to 90 bpm
3. Any laboratory value outside the reference range that the investigator considers to be of clinical relevance
4. Any evidence of a concomitant disease judged as clinically relevant by the investigator
5. Gastrointestinal, hepatic, renal, respiratory, cardiovascular, metabolic, immunological or hormonal disorders
6. Diseases of the central nervous system (including but not limited to any kind of seizures or stroke), migraine, and other relevant neurological or psychiatric disorders
7. History of relevant orthostatic hypotension, fainting spells, or blackouts
8. Chronic or relevant acute infections

9. History of relevant allergy or hypersensitivity (including allergy to the trial medication or its excipients)
10. Use of drugs (including any biological agent) with a long half-life (more than 24 h) within 30 days or less than 10 half-lives of the respective drug (whichever is greater) prior to administration of trial medication
11. Within 10 days prior to administration of trial medication, use of drugs that might reasonably influence the results of the trial or that might prolong the QT/QTc interval
12. Participation in another trial where an investigational drug has been administered within 60 days or 10 half-lives (whichever is greater) prior to planned administration of trial medication
13. Smoker
14. Ex-smoker who has stopped smoking less than one year prior to enrolment and/or who has a history of equal or more than 10 pack years
15. Alcohol abuse (consumption of more 30 g per day)
16. Drug abuse or positive drug screening
17. Blood donation of more than 100 mL within 30 days prior to administration of trial medication or intended donation during the trial
18. Intention to perform excessive physical activities within one week prior to administration of trial medication or during the trial
19. Inability to comply with dietary regimen of trial site

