20. A marked baseline prolongation of QT/QTc interval (such as QTc intervals that are repeatedly greater than 450 ms) or any other relevant ECG finding at screening
21. A history of additional risk factors for Torsades de Pointes (such as heart failure, hypokalemia, or family history of Long QT Syndrome)
22. Subject is assessed as unsuitable for inclusion by the investigator, for instance, because considered not able to understand and comply with study requirements, or has a condition that would not allow safe participation in the study

23. History of tuberculosis infection and/or a confirmed positive Quantiferon TB-Gold test
24. Subjects who in the investigator's judgement are perceived as having an excessive risk of thromboembolism (TE) for example because of a personal history and/or a first degree relative with a personal history with onset under the age of 55 of significant TE, including but not limited to deep vein thrombosis, pulmonary embolism, cortical sinus thrombosis, coronary and cerebrovascular events, cardiovascular disease, and peripheral arterial insufficiency
25. Abnormal results of coagulation values indicating an increased risk for bleeding or thromboembolism or complicating the safety evaluation during the study as determined by the investigator.
26. Deficiency of antithrombin III or protein S or protein C
27. Clinically relevant abnormal result of oral glucose tolerance test at baseline
28. Estimated glomerular filtration rate (eGFR) according to CKD-EPI formula < 90 mL/ min at screening ([R12-1392](#))

29. Urinary albumin/creatinine ratio (UACR) \geq 30 mg albumin / g creatinine at screening

For study restrictions, refer to [Section 4.2.2](#).

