4.2.2.2 Restrictions on diet and life style

While admitted to the trial site the subjects are restricted from consuming any other foods or drinks than those provided by the staff. Standardised meals will be served at the time points described in the [Flow Chart](#). No food is allowed from at least 10 hours before drug administration until at least 30 minutes after end of infusion.

From drug administration until 30 min after end of infusion, no liquid intake is allowed. During the days of urine collection, total fluid intake should be at least 1.5 litres and should not exceed 3.5 litres.

Alcoholic beverages are not allowed from five days before the administration of trial drug until after trial assessments of Day 29 have been completed. Thereafter subjects may drink up to 20 g alcohol per day, corresponding to 0.5 L beer or 0.2 L white wine.

Dietary supplements and products including St. John's wort (*Hypericum perforatum*) are not permitted starting 7 days before the administration of trial medication until after the end of trial examination.

During in-house confinement at the trial site, smoking and consumption of methylxanthine-containing drinks or foods (such as coffee, tea, cola, energy drinks, and chocolate) is not allowed.

Excessive physical activity (such as competitive sport) should be avoided starting 7 days before the administration of trial medication until the end of trial examination.

Direct exposure to the sun or exposure to solarium radiation should be avoided during the entire study.

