5.2.3.1 Oral glucose tolerance test (oGTT)

An oGTT will be performed on the morning of Day -5 to -1 (baseline) and Day 29. After blood drawing for determination of fasting plasma glucose and serum insulin, 75 g of glucose will be dissolved in 200 mL water and swallowed by the subject. Thirty minutes, 1, 2 and 3 hours after intake of the glucose solution, further blood samples will be taken for glucose and insulin measurement. Blood samples for glucose measurements will be drawn in a 2 mL sodium fluoride (NaF) tube. Blood samples for insulin measurements will be drawn in a 2.5 mL serum tube.

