Changes in AUCs for glucose and insulin (oGTT measurements) from baseline to post-treatment will be compared between BI 655088 and placebo.

Descriptive statistics of bleeding time at the time points given in the [Flow Chart](#) and for the difference from baseline will be provided.

Descriptive statistics of vital signs and for the difference from baseline will be presented per planned time. ECG data will not be listed but clinically relevant abnormal findings will be reported as adverse events.

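### The permitted baseline oGTT window opens before the alcohol, supplement and exercise restrictions start, so baseline test conditions can differ between subjects

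*Protocol*

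**What the plan says.** Section 5.2.3.1 fixes the test days: "An oGTT will be performed on the morning of Day -5 to -1 (baseline) and Day 29". Section 6.1 widens the baseline side, stating that "Oral glucose tolerance test at baseline may be done within 8 days prior to the drug administration" and that "the acceptable deviation from Day -5 will be -3 days".

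The lifestyle rules in Section 4.2.2.2 have their own start dates. For alcohol: "Alcoholic beverages are not allowed from five days before the administration of trial drug until after trial assessments of Day 29 have been completed". For exercise: "Excessive physical activity (such as competitive sport) should be avoided starting 7 days before the administration of trial medication". Dietary supplements are also barred from seven days before dosing. Exclusion criterion 18 uses the same one-week span for intended excessive activity. Before the alcohol rule starts, the only limit is criterion 15, which excludes intake above 30 g per day.

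The baseline test has two uses. Criterion 27 excludes a subject with a "Clinically relevant abnormal result of oral glucose tolerance test at baseline". Section 7.3.3 states: "Changes in AUCs for glucose and insulin (oGTT measurements) from baseline to post-treatment will be compared between BI 655088 and placebo". The same section pools placebo subjects over all dose groups.

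**The concern.** The window in Section 6.1 and the restrictions in Section 4.2.2.2 were not set to match. A site using the early part of the window may test a man who is still free to drink up to the criterion 15 limit. On Day -8 he is also free of the exercise and supplement rules. Another subject in the same dose group may be tested on Day -2 under all three restrictions. Both results then serve as baseline on equal terms.

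Two things are at stake. Eligibility under criterion 27 is judged under conditions that vary between subjects. And the change to Day 29 mixes any drug effect with the end of drinking or training in some subjects but not in others. Section 7.3.3 plans individual time courses and descriptive comparisons by group, and with six active subjects per dose group a few such baselines can be visible.

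**Working it through.** **Day count.** Dosing is on Day 1. Section 6.1 equates 8 days before dosing with Day -5 minus 3 days: -5 - 3 = -8. The two statements agree if there is no Day 0, so Day -k lies k days before dosing. The alcohol restriction then starts on Day -5, and the supplement and exercise restrictions on Day -7.

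**Window against restrictions.**

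| Baseline oGTT day | Alcohol rule in force | Supplement and exercise rules in force |
|---|---|---|
| -8 | no | no |
| -7, -6 | no | yes |
| -5 | first day | yes |
| -4 to -1 | yes | yes |
| Day 29, for comparison | yes | yes |

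Three of eight permitted days (-8, -7, -6) precede the alcohol rule, and one of eight (-8) precedes all three rules.

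**Effect on the contrast with placebo.** Let *s* be the shift in AUC change caused by an unrestricted baseline, assumed equal in every affected subject. The documents give no value for *s*. If a share *a* of the active subjects and a share *b* of the placebo subjects are tested early, the difference in mean change is shifted by (a - b) × s. Each dose group has 6 active and 2 placebo subjects, so pooled placebo is 6 × 2 = 12. By Sections 2.3 and 3.1, the second cohort of each group is two subjects, both active.

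| Assumed use of Days -8 to -6 | a | b | Shift |
|---|---|---|---|
| Equal shares in both arms | p | p | 0 |
| Only the second cohort of one dose group; that group against pooled placebo | 2/6 | 0/12 | s/3 |
| All 8 subjects of one dose group and nobody else; that group against pooled placebo | 6/6 | 2/12 | 5s/6 |

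In the last row the group's own two placebo subjects would give 1 - 1 = 0, so that shift comes from pooling. These are possible patterns. Nothing in the documents shows that any of them occurred.

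**Effect on variability.** Under the same assumption, a share *p* tested early adds p(1 - p)s² to the variance of the change within a group. The maximum is s²/4, at p = 1/2.

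**The case against.** The case for leaving the text alone has weight. Placebo subjects follow the same rules and are spread equally over dose groups, so a shift common to both arms cancels in expectation. The oGTT is a further criterion of interest, not the primary endpoint, and the analysis is descriptive. Laboratory samples are taken after at least 10 h of fasting. Criterion 27 rests on clinical judgement, and screening also includes plasma glucose and HbA1c. Criterion 11 bars drugs that might influence the results for 10 days before dosing, which covers Day -8, although it does not expressly cover supplements. The amendment log shows that the wider window was introduced on purpose, for logistics. No passage says that the lifestyle rules exist to standardise the oGTT.

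Most of this stands, and it limits the point to a minor one. It does not close the gap. The logistic reason explains the wider window but not why the restrictions stayed where they were. Cancellation depends on balanced use of the early days, which the design does not secure: Section 4.1.2 fills cohorts by subjects' availability, and the second cohort has no placebo subject.

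A reader might go further and set no abstinence at an early baseline against about 33 days (5 + 28) of enforced abstinence at Day 29, and blame the window. The documents do not support that. On the ordinary Day -5 to -1 schedule, required abstinence is already only 0 to 4 days against the same 33, so the window does not create the contrast. Nor is abstinence strictly enforced: after at least 48 h in-house the visits are ambulatory, and only the breath test at admission on Day -1 is fixed.

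**Conclusion.** The point holds as a misalignment between Sections 4.2.2.2 and 6.1. Three of eight permitted baseline days precede the alcohol rule, and one precedes all three rules. Baseline conditions can therefore differ between subjects for a test that decides eligibility and anchors the AUC change.

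A reader might infer a systematic bias in the comparison with placebo; that does not follow. With balanced use of the early days the expected shift is zero. With unequal use it is (a - b) times an effect whose size the documents do not give. The sure cost is lost uniformity at baseline; how much variability that adds depends on the same unknown effect.

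This rests on three assumptions: there is no Day 0, as the wording of Section 6.1 implies; some subjects are in fact tested on Day -8 to -6; and drinking, training or supplements affect the oGTT at all. The Flow Chart was not part of the text reviewed; a footnote there that ties the restrictions to the test day would settle the matter. Priority: minor.

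**What to change.** Reconcile Section 4.2.2.2, exclusion criterion 18, Section 5.2.3.1 and Section 6.1 so that every permitted baseline oGTT falls within the restricted period. One way is to start the three restrictions no later than the earliest permitted oGTT day. Section 5.2.3.1 should then state the same baseline window as Section 6.1.

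Cost: short edits in those places and in the subject instructions. With a start on Day -8, the alcohol rule begins 8 - 5 = 3 days earlier and the supplement and exercise rules 8 - 7 = 1 day earlier. This applies to every subject, including those tested late in the window. No visit or test is added, and the site keeps its scheduling freedom.

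The change makes baselines more alike across subjects. It does not equalise the length of abstinence between baseline and Day 29, and should not be presented as doing so.
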